## 9.5 Optional Open-label Extension Period

Patients who consent to the optional OLE will enter the OLE under the circumstances defined in section 6.3.

Treatment with Lu AF82422 will continue on the first visit of the OLE (Visit 1E) which will take place at the same day as the EoTDBP Visit, or as soon as possible thereafter, but no later than 5 months after the EoTDBP Visit, and will be enrolled into the OLE no later than the end of Q1 2024. If a Safety Follow-up Visit for the DBP is due before the OLE is implemented, it should be completed per Panel 2. The patient could afterwards enter the OLE and treatment could continue for a planned period of 96 weeks. OLE procedures will be performed as presented in Panel 3.

For patients who enter the OLE and have the first visit of the OLE at the same day of the EoTDBP visit, clinical assessments would not have to be repeated. In that case, data will automatically be transferred. However, in case of >7 days in between the EoTDBP visit and the first visit of the OLE, clinical assessments would have to be re-performed.

## 9.5.1 End-of-Treatment Visit – Optional Open-label Extension Period

Patients who enter the OLE will receive the first open-label dose of Lu AF82422 (Visit 1E) on the same day as the EoTDBP or as soon as possible thereafter and the last dose on Visit 24E (Week 92E); EoT in the 96-week OLE is at Visit 25E (Week 96E).

# 9.5.2 Safety Follow-up Visit Open-label Extension Period 20 Weeks After Last Dose of IMP

A Safety Follow-up Visit of the extension period (SFU-E) is conducted to capture new adverse events that occur during the Safety Follow-up Period as well as to follow-up on the outcome of adverse events on-going at the end of the treatment period. In addition, the following will be collected; blood and urine samples for clinical safety laboratory tests, blood sampling for IMP quantification and ADA, vital signs, physical and neurological examination, C-SSRS assessment, concomitant medication and pregnancy test. The Safety Follow-up must be conducted as a visit to the site. The Safety Follow-up Visit is scheduled 20 weeks after the last dose of IMP.

For adverse events that were on-going at the EoTOLE, or Withdrawal Visit and that resolved during the Safety Follow-up Period, the stop date must be recorded. For non-serious adverse events still on-going at the Safety Follow-up Visit, the *On-going Adverse Event* checkbox on

the Adverse Event Form must be ticked. SAEs must be followed until resolution, or the outcome is known.

The Safety Follow-up Visit for patients who withdraw consent must be performed, if at all possible; any information collected will only be recorded in the patients' medical records.

For details of assessments to be conducted at the Safety Follow-up Visit, see Panel 3.

#### 9.6 Withdrawal Visit

Patients who withdraw from the study prior to the respective EoT Visit for the treatment period (ie, EoTDBP or EoTOLE) will be asked to attend a Withdrawal Visit and Safety Follow-up Visit, if at all possible. If the patient cannot attend the site physically for the Withdrawal Visit, and the visit would then not be performed, the visit should be performed as a remote or Telemedicine visit with assessments performed as described in the "COVID-19 Mitigation Plan", if possible. The Withdrawal Visit must be scheduled as soon as possible after withdrawal.

No new information will be collected from patients who withdraw from the study, except information collected in relation to the scheduled Withdrawal Visit and the Safety Follow-up Visit 20 weeks after last dose of IMP or needed for the follow-up of adverse events (section 11.5).

MRI scanning is only to be performed as an EoT/withdrawal procedure if it was not performed within the last 8 weeks.

Patients who withdraw during a period with fall diary entries must return the diary at the Withdrawal Visit.

Patients who withdraw during a period with objective sensor-based assessments must return the sensor(s) at the Withdrawal Visit.

The Exit interview will be conducted within 3 weeks after the Withdrawal Visit for patients who have been in the DBP for at least 48 weeks prior to withdrawal. For patients who withdraw from study treatment after Week 48 in the DBP and complete an Exit interview, patients may be contacted to participate in a Study Experience interview.

The reason for withdrawal must be recorded in the eCRF.

For a patient who withdraws consent:

• if the patient withdraws consent during a visit and then agrees to it being the final visit, the investigator will complete the visit as the Withdrawal Visit and all the data collected up to and including that visit will be used.

- if the patient withdraws consent during a telephone conversation, the investigator will ask the patient if he or she will attend a Withdrawal Visits. If the patient:
  - -agrees to attend a Withdrawal Visit, all the data collected up to and including these visits will be used
  - -refuses to attend a Withdrawal Visit, the investigator should attempt to follow the patient's safety and future treatment; any information collected will only be recorded in the patient's medical records
- if the patient explicitly requests that the patient's data collected from the time of withdrawal of consent onwards not be used, this will be respected.

It is planned to conduct the same assessments as for the EoT if the patient is withdrawn during the DBP (Visit 18, for list of assessments see Panel 2).

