#### 6.4 Withdrawal Criteria

A patient must be withdrawn from the study if:

- The patient withdraws consent (defined as a patient **explicitly** takes back his or her consent); section 9.6 states how the patient's data will be handled
- The patient has been randomized in error and has not been administered IMP
- Withdrawal of patients enrolled in error and who have received the IMP should be based on a case-by-case evaluation of the individual risk/benefit. The decision about the administration of more doses of Lu AF82422 will be based on an individual risk/benefit assessment as judged by the investigator
- The patient can no longer attend study visits due to MSA disease progression.
- The patient is lost to follow-up (defined as a patient who fails to comply with scheduled study visits or contact, who has not actively withdrawn from the study, and for whom no alternative contact information is available [this implies that at least two documented attempts have been made to contact the patient])

A patient must be withdrawn from treatment if:

- The patient experiences any systemic hypersensitivity reaction to IMP infusion which are confirmed as anaphylactic reaction by a clinically relevant increase of serum total tryptase from baseline level (see section 11.1.3)
- The patient experiences any severe and/or serious systemic hypersensitivity reactions even though the serum total tryptase does not confirm an anaphylactic reaction
- The patient experiences an adverse event that, in the opinion of the investigator or sponsor's medical expert, contraindicates further dosing
- The investigator considers it, for safety, lack of efficacy, and/or study compliance reasons, in the best interests of the patient that he or she be withdrawn from treatment
- Any site personnel breaks the randomization code for that patient
- The patient becomes pregnant
- The patient has a serum ALT or AST value >3 times the upper limit of the reference range and a serum total bilirubin value >2 times the upper limit of the reference range
- The patient has a serum ALT or AST value >5 times the upper limit of the reference range that is confirmed by testing <2 weeks later
- The patient has a QTcF interval >500 ms confirmed on repeat, if the repeat is done within 72 hours; the decision to withdraw the patient may be postponed until a repeat ECG is taken, if it is taken within 72 hours during the DBP.
- A patient may be withdrawn from the study if:

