#### 11.5 Treatment and Follow-up of Adverse Events

Patients with adverse events must be treated in accordance with usual clinical practice at the discretion of the investigator.

Study 18331A - Clinical Study Protocol

Page 96 of 131

The investigator must follow-up on non-SAEs until resolution or completion of a Safety Follow-up Visit, whichever comes first. At the Safety Follow-up Visit, information on new adverse events (non-serious and serious adverse events), if any, and stop dates for previously reported adverse events must be recorded.

The investigator must follow-up on all SAEs until the patient has recovered, stabilized, or recovered with sequelae, and report to Lundbeck all relevant new information using the same procedures and timelines as those for the initial *Serious Adverse Event Form*.

SAEs that are spontaneously reported by a patient to the investigator after completion of the Safety Follow-up Visit must be handled in the same manner as SAEs that occur during the study. These SAEs will be recorded in the Lundbeck safety database.

Patients with a clinically significant out-of-range clinical safety laboratory test value at an EoT or any Withdrawal Visit must be followed in accordance with usual clinical practice. If the clinically significant out-of-range clinical safety laboratory test value has not normalized or stabilized or a diagnosis or a reasonable explanation has not been established by the Safety Follow-up Visit, the investigator must decide whether further follow-up visits are required (this may include an additional medical examination and/or additional blood sampling). If further follow-up visits are made, these must be documented in the patient's medical records and not in the eCRF.

Patients who withdraw due to an elevated AST or ALT value (see section 6.4) must be followed until the values normalize or stabilize or a diagnosis or a reasonable explanation has been established. Additional medical examinations (for example, ultrasound scanning and/or sampling for serology, conjugated bilirubin, prothrombin time) should be considered. A gastroenterology or hepatology consultation should also be considered.

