14.3.5 Sensitivity Analyses of the Primary Endpoint

Handling of Missing Data

The following sensitivity analyses will be performed in case of drop-out/withdrawal/death, where the below rules will be applied for the visit following the event for subjects not having

complete data from the Withdrawal Visit, assuming that intermediate missingness will be 'missing at random':

- For withdrawal due to death, impute individual missing UMSARS items as worst possible score in case of death.
- For withdrawal due to other reasons, impute individual missing UMSARS items as worst observed within-subject value for the specific item at any post-IMP time point.
- For withdrawal due to other reasons, impute individual missing UMSARS items as the worst value observed within the combined treatment and control arms at any post-IMP time point.

Two analyses will be performed in both cases using the above strategy to handle withdrawal due death. Following each of the above strategies for handling withdrawals due to other reasons will then be applied.

To explore further the impact of death, a non-parametric joint-rank analysis will be performed to account for informatively missing data by ranking patients based jointly on their Week 48 UMSARS score (UMSARS TS and mUMSARS) and 48-week survival, i.e., time-to-death. Such analysis corresponds to a composite strategy. In case of missing Week 48 data for survivors, Multiple Imputation (MI) will be performed in which the remaining missing data will be imputed corresponding to a missing-at-random assumption.

Missing data for UMSARS Week 12 up to Week 48 will be addressed by using Multiple Imputation. Missing data will be imputed using a sequential regression-based multiple imputation method, based on the imputation models established from the corresponding randomized treatment group. Example SAS code for this imputation can be found in Appendix II.

200 imputed datasets will be created, which will each be analysed and combined as follow.

Define score, u_{ij} , which is chosen to reflect whether patient i has had the more favourable UMSARS score than patient j. In the case where both patient i and j died prior to the Week 48 assessment:

- $u_{ij} = 1$ in the case where patient i died after patient j
- $u_{ij} = -1$ in the case where patient i died before patient j
- $u_{ij} = 0$ in the case where it cannot be determined who died first

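### Planned contact ends 20 weeks after the last dose, so early withdrawals have no planned survival status at Week 48 for the joint-rank sensitivity analysis, and the worst-score rules do not clearly cover a death after withdrawal

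*Protocol*

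**What the plan says.** **Collection.** Protocol 9.6: "No new information will be collected from patients who withdraw from the study, except information collected in relation to the scheduled Withdrawal Visit". The sentence continues with the Safety Follow-up Visit 20 weeks after the last dose and whatever adverse-event follow-up requires. Protocol 11.5 supplies two further routes. One is that "The investigator must follow-up on all SAEs until the patient has recovered, stabilized, or recovered with sequelae". The other covers late reports: "SAEs that are spontaneously reported by a patient to the investigator after completion of the Safety Follow-up Visit must be handled in the same manner", that is, like those arising while the patient is in the study. SAP 3.3 classes a patient who stops treatment in the double-blind period (DBP) as withdrawn from the study. The open-label entry criteria in Protocol 6.3 exclude such patients, so the extension adds no contact for them. SAP 16.9 censors time-to-death at the last safety follow-up visit.

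**Joint-rank analysis.** SAP 14.3.5 plans "ranking patients based jointly on their Week 48 UMSARS score (UMSARS TS and mUMSARS) and 48-week survival, i.e., time-to-death". The pairwise scores cover three situations: both patients died before Week 48, one died, or both are alive. There is a tie rule for two deaths whose order is unknown, but none for a patient whose survival is unknown. "In case of missing Week 48 data for survivors, Multiple Imputation (MI) will be performed", under missing-at-random, with models built within the patient's randomised arm.

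**Worst-score rules.** SAP 14.3.5: "For withdrawal due to death, impute individual missing UMSARS items as worst possible score in case of death". The imputation applies only to patients without complete Withdrawal Visit data. SAP 24.1.1 makes a similar exception for patients whose drop-out is due to death. Its next sentence speaks of death more generally and places the worst score at the visit after the date of death.

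**The concern.** Two gaps follow from reading these provisions together.

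- The joint-rank analysis needs a fact, alive or dead at Week 48, that the protocol does not plan to collect for early withdrawals. A patient with no recorded death can enter only as a survivor, with a score imputed from others in the same arm. An unrecorded death then moves from the bottom of the ranking to a survivor's rank. This flatters active if the death was on active, and placebo if it was on placebo.
- The worst-score rules depend on the recorded reason for leaving, not on the death. A patient who withdraws alive and is known to have died some weeks later falls under the rule for other reasons, or gets no imputation if the Withdrawal Visit was complete. This gap exists even where collection is perfect.

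Protocol 17.9.3 says the sensitivity analyses should focus in particular on deaths and on drop-outs without follow-up data, so these are the patients the analyses are meant to address.

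**Working it through.** **1. The plan's own timeline.** Screening to baseline is 6 weeks, and the Safety Follow-up is 20 weeks after the last dose. A last dose at Week 44 gives 6 + 44 + 20 = 70 weeks; at Week 68, 6 + 68 + 20 = 94 weeks. Both match the stated 70 to 94 weeks for patients not entering the extension.

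**2. Gap to Week 48.** Gap = 48 − (week of last dose + 20), where positive.

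| Last dose (week) | 0 | 4 | 8 | 12 | 16 | 20 | 24 | 28 or later |
|---|---|---|---|---|---|---|---|---|
| Planned last contact (week) | 20 | 24 | 28 | 32 | 36 | 40 | 44 | 48 or later |
| Uncovered weeks | 28 | 24 | 20 | 16 | 12 | 8 | 4 | 0 |

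The visit window of ±7 days blurs the edges. The mean gap for Weeks 0 to 24, equally weighted, is 16 weeks. Patients lost to follow-up, or who withdraw consent and refuse visits, can have a longer gap.

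**3. Patients affected.** Protocol 17.12 allows 20% drop-out: 0.20 × 60 = 12. The documents do not give its timing. If withdrawal is uniform over T weeks, the share with a last dose at Weeks 0 to 24 is 28/T:

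- T = 48: 12 × 28/48 = 7.0
- T = 60: 12 × 28/60 = 5.6
- T = 72: 12 × 28/72 = 4.7

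Exponential timing gives 5.0 to 7.3. The FAS (SAP section 5) requires a post-baseline UMSARS, first scheduled at Week 12, so some of the earliest withdrawals are not ranked at all.

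**4. Expected unrecorded deaths.** No death rate is given, so this is a range over assumptions. For an assumed 48-week risk a in these patients and the mean gap, p = 1 − (1 − a)^(16/48).

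| Assumed a | p | Expected deaths, n = 5 to 7 | Chance of at least one |
|---|---|---|---|
| 5% | 0.017 | 0.08–0.12 | 8–11% |
| 10% | 0.035 | 0.17–0.24 | 16–22% |
| 20% | 0.072 | 0.36–0.50 | 31–41% |
| 40% | 0.157 | 0.78–1.10 | 57–70% |

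This counts every death in the gap as unrecorded; SAE reporting would reduce it.

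**5. Effect of one misclassified death.** With 60 patients and no ties, the U scores run from −59 to 59 in steps of 2. Their SD is √[(60² − 1)/3 × 60/59] = 34.9, so the SE of the arm difference is 34.9 × √(1/40 + 1/20) = 9.6. Let q be the share of the others ranked worse than the patient before the move. Going to the bottom costs the patient 2 × 59q and gives each patient overtaken 2 points. With no treatment effect:

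- Placebo death: the placebo mean changes by (−118q + 38q)/20 = −4q and the active mean by +2q, a shift of 6q.
- Active death: the active mean changes by (−118q + 78q)/40 = −q and the placebo mean by +2q, a shift of 3q.

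| Imputed position | Placebo death | Active death |
|---|---|---|
| Middle (q = 0.5) | 3.0/9.6 = 0.31 SE | 1.5/9.6 = 0.16 SE |
| 75th percentile of severity (q = 0.25) | 0.16 SE | 0.08 SE |
| 90th percentile (q = 0.10) | 0.06 SE | 0.03 SE |

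A simulation without treatment effect gave 2.97/9.56 = 0.31 for the placebo case. A second simulation assumed active better by 0.62 SD. There the shift in the t statistic was about 0.23 for a placebo death and 0.24 for an active one, so the 0.16 belongs to the no-effect case.

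**The case against.** The strongest reply is that little is at stake.

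- **Some deaths will surface.** Worsening of MSA that meets a seriousness criterion is reportable (Protocol 11.1.1), open SAEs are followed, and spontaneous reports are accepted. This stands, but it is not a planned survival check.
- **Few deaths are expected.** Eligibility requires an anticipated survival of at least 3 years and a UMSARS Part I score of 16 or less. This stands as a reason to favour the lower rows of the death-risk table, though the documents do not settle the rate.
- **Imputation is not blind to severity.** Regression on earlier scores would place a fast progressor well down the ranking, which shrinks the shift. This stands.
- **A harsh bound already exists.** One analysis in SAP 14.3.5 gives withdrawals for other reasons without complete Withdrawal Visit data the worst item value seen in either arm. This stands for those patients, but not for those with a complete visit, and it does not enter the joint rank.
- **The intercurrent-event text is redacted.** It may determine how death after withdrawal should count, so the rules need to be aligned with it. A handling strategy would not by itself supply survival status.

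A reader might infer from Protocol 6.4 ("The patient can no longer attend study visits due to MSA disease progression") that the patients nearest death are forced out early. The amendment summary shows that this criterion was added in Edition 6.0, the edition that lengthened the extension, so it probably did not govern many withdrawals by Week 24 of the DBP. The argument should not rest on it.

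**Conclusion.** The point holds for the sensitivity analyses of death. No survival check is planned between the Safety Follow-up Visit and Week 48 for last doses at Weeks 0 to 24. The joint-rank scoring has no place for unknown status, and the worst-score rules do not clearly reach a death after an alive withdrawal. That an unrecorded death is ranked as a survivor follows from the scoring rules; the SAP does not say so outright.

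The size is modest. The count of 5 to 7 patients rests on the planned drop-out rate and an assumed spread of timing. The per-death limits of about 0.3 SE (placebo) and 0.16 SE (active) assume no treatment effect and an imputed rank at the middle or worse. How many deaths would be missed cannot be derived from the documents.

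A reader might infer that the primary result is biased, or that any finding of robustness to death would be worthless. The documents support neither. The primary model uses observed data without imputation, and at low assumed death risks most realisations would contain no unrecorded death. What is missing is a way to show how many patients have unknown status and how much that could matter.

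**What to change.** 1. In SAP 14.3.5 and 24.1.1, key the death rule of these sensitivity analyses to a date of death within the patient's planned DBP, whatever withdrawal reason was recorded and whether or not a Withdrawal Visit was completed. Word it consistently with the redacted intercurrent-event strategy.
2. In the joint-rank analysis, impute as survivors only patients known to be alive at Week 48. Report the number with unknown status by arm, and add a bounding run that counts them as deaths.
3. Where consent allows, add vital status and date of death, at nominal Week 48 and at DBP close-out, to the exceptions in Protocol 9.6, obtained by a call or from site records.

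Items 1 and 2 are SAP wording, need no new data and can be settled before unblinding. Item 3 needs a small protocol amendment with ethics committee or IRB review and consent wording, plus a few calls for roughly 12 expected drop-outs, some of them to families of patients who have left the study. If item 3 proves impractical, items 1 and 2 are still worth making.

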#### 9.7 Unscheduled Visit

If needed, an unscheduled visit can be performed between Randomization and the Safety Follow-up Visit for any of the safety assessments:

- Blood and urine sampling for clinical safety laboratory tests
- Blood sampling for ADA
- Vital signs
- Weight
- Examinations (physical, neurological)
- ECG
- MRI scan for safety
- C-SSRS
- Serum total tryptase sample to evaluate baseline tryptase level in the event of an anaphylactic reaction or a systemic hypersensitivity reaction

Adverse events must always be collected at an unscheduled visit.

## 9.8 End-of-study Definition

The end of the study for an individual patient is defined as the last protocol-specified contact with that patient. The overall end of the study is defined as the last protocol-specified contact with the last patient on-going in the study.

## 10 Assessments

## 10.1 Screening and Baseline Procedures and Assessments

## 10.1.1 Randomization Visit (Visit 2, Week -2)

Randomization will be performed at Visit 2 after checking inclusion/exclusion criteria, as well as signs and symptoms present. The tablet to record falls (fall diary) and other patient-reported outcomes (PROs) will be handed out. All PROs will be administered electronically by using a tablet. The patients and their caregivers will be trained on how to use the electronic PROs (ePROS) by site staff who have adequate experience with MSA patients and have received adequate training on good standards in providing guidance to patients on how to use the ePROs.

In exceptional cases, the visit interval between the Screening and Randomization Visits may be extended with consent from the Lundbeck medical expert/medical monitor, provided the Lundbeck medical expert accepts the rationale provided for the extension. The full list of assessments at the Randomization Visit are summarized in Panel 2.

